**Interindividual Postexercise Hypotension Response in Morbid
Obesity**

NCT05504629

Date: March 17th, 2021

Study documents

Scientific background: Physical inactivity and sedentary behaviour [*i.e.*, Do not adhere to international physical activity guidelines of a minimum of 150 min of physical activity ^{1]} together with other lifestyle conditions (*i.e.*, unhealthy nutrition, or poor sleep time) promote obesity, and cardiometabolic diseases such as type 2 diabetes mellitus (T2DM), and arterial hypertension (HTN) ², two major diseases in the modernity, and of high prevalence in populations with excessive of adiposity such as those with morbid obesity ². Unfortunately, metabolic syndrome (MetS), another more complex cardiometabolic square that implies also obesity, poor glucose control, high blood pressure, dyslipidaemia, and high triglycerides in plasma exacerbates the risk for suffering from cardiovascular disease particularly those with morbid obesity who are candidates for bariatric surgery ³. For example, a relevant meta-analysis of 87 studies with a sample of ($n=951.083$) showed that MetS risk factors were associated with an increased risk for cardiovascular disease (CVD) (Relative Risk, [RR]= 2.35), CVD mortality (RR= 2.40), myocardial infarction (RR= 1.99, stroke (RR= 2.27), and all-cause mortality (RR= 1.58) ⁴. Patients with Morbid obesity are a particular population that suffers from multiple risks for CVD, including MetS, endothelial dysfunction, as well as HTN and T2DM risk factors, all of these related to a better or worse profile to deal with success and better recovery period after bariatric surgery ¹. From the National Health Survey of Chile, there was described that morbid obesity is a worrying concern in women in childbearing ages 20 to 45 y, showing almost no changes from 2003 (2.2%) to 2009-10 Survey (2.1%) ⁵. Thus, among these patients, to acquire the bariatric surgery benefit, these increase their possibilities to lose excess weight near to ~50%, to recover their overall cardiometabolic health ⁶, and this has been strongly related to improvements in their quality of life ⁷.

From here, lifestyle interventions such as exercise training play a key role⁸⁻¹⁰, and relevant international organizations such as the American College of Sports Medicine¹, and the European Association For The Study of Obesity Physical Activity Working Group¹¹ have recently highlighted their benefits before and after bariatric surgery. Exercise training is a known but poorly used strategy for controlling cardiometabolic risk in populations with T2DM, HTN, and MetS^{8,12}. At least in the blood pressure, and vascular context, exercise training decrease chronic, and acute blood pressure levels¹³⁻¹⁶. For example, a single session of endurance training (ET) (also known as moderate-intensity continuous training), decreased the 24 h blood pressure¹⁷, being the magnitude of this effect is superior in subjects with higher blood pressure (systolic [SBP]/diastolic [DBP] $-16.1/-7.5$ mmHg)¹⁷ and to those with HTN controlled and HTN not so controlled^{18,19}, but clearly, less marked in healthy normotensive subjects (SBP/DBP $-5.6/-3.1$ mmHg)²⁰. These effects have been confirmed by relevant meta-analysis where long-term ET has been a recognized strategy to get these goals in pre- and hypertensive populations^{21,22}. On the other hand, RT also decreases blood pressure, where only 45 minutes after an acute resistance training (RT) session in HTN subjects (SBP/DBP $-22.0/-8.0$ mmHg), and this have been also confirmed by other relevant meta-analyses where summarize blood pressure decreases after RT in -4.4 mmHg²³. Recently, and in similar coherence with ET, the RT modality has reported higher magnitude in BP reduction in subjects with elevated (SBP/DBP $-12.0/-4.0$ mmHg), than healthy subjects (SBP/DBP $-4.0/-1.0$ mmHg)²⁴. From here, the postexercise hypotension (PEH) [*i.e.*, defined as a reduction in systolic and/or diastolic arterial blood below control levels after a single but of exercise²⁵] is the first vascular benefits immediately after exercise acquire a meaningful relevance, in terms that the summary of physiological adaptations by each exercise session can promote a renova of the vasculature structure using molecular mechanisms²⁶. Thus, as

after both ET and RT, there are a number of evidence reporting the PEH benefits in different cohorts, but unfortunately there is little evidence reporting this phenomenon after concurrent training (CT), and yet less knowledge in population with MetS risk factors, as those with morbid obesity.

On the other hand, the main PEH studies report data in terms of ‘average data’, and it is well known that there is a wide interindividual variability to exercise training²⁷, being a need for the report of data at an individual level. Thus, considering that there is little knowledge about the role of the order (*i.e.*, starting by ET plus RT or by RT plus ET) in the CT session, taking into account that risk factors for MetS increase the risk for vascular damage and CVD. This study will follow the CONSORT guidelines for randomised trials, will be developed in accordance with the Declaration of Helsinki (2013), and has been approved by the Ethical Committee of the Universidad de La Frontera, Temuco, Chile (DI18-0043 Project, ACTA N° 080_21). **Design:** A quasi-experimental clinical study. **Methods:** Patients with morbid obesity were invited for participating by a public invitation and directly to the Morbidly Obesity Association of Temuco, City, Chile (OBEMOB). After providing wide information and feedback about the risks/benefits of the intervention, all participants signed informed consent for participating in the study. We recruited diagnosed morbid obesity sedentary/physically inactive subjects (body mass index [BMI] between ≥ 40 kg/m²; aged 30 to 55 years) that were under the OBEMOB institution, who were assigned for convenience in 1:1 allocation to a CT group of endurance [ET] plus resistance training [RT] (ET+RT; $n=17$; BMI 47.8 ± 16.7) or resistance training plus endurance training group (RT+ET; $n=13$; BMI 43.0 ± 8.0). Patients were recruited between 2020 and 2021 year from the above non-governmental mentioned institution. All participants were part of the lifestyle program

previous to the possibility of receiving the bariatric surgery benefit for this disease condition from the Health Ministry of Chile (MINSAL).

REFERENCES

3. Bellicha A, van Baak MA, Battista F, et al. Effect of exercise training before and after bariatric surgery: A systematic review and meta-analysis. *Obesity Reviews* 2021; **22**: e13296.

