potential differences between ET+RT vs. RT+ET. Additionally, delta changes (Δ) from pre-post were calculated to SBP, DBP, MAP, HR, and PP outcomes to test by the independent Student *t*-test differences between groups, where optionally the non-parametric Wilcoxon test was applied for non-parametric variables. The Cohen *d* effect size was obtained with threshold values at 0.20, 0.60, 1.2, and 2.0 for small, moderate, large, and very large effects, respectively²⁸. These analyses were carried out by the statistical software Graph Pad Prism 8.0 software (Graph Pad Software, San Diego, CA, USA). After this, all results in Δ changes of the sum of SBP $\sum\Delta$ SBP was individualized and presented in quartile to be categorized in those participants ‘nonresponders’ (NRs; Q1 with SBP < -1 mmHg), ‘low’ responders (LRs; Q2 with SBP -1 to -9.9 mmHg), ‘moderate’ responders (MRs; Q3 with SBP -10 to -18 mmHg), and ‘high’ responders (HRs; Q4 with SBP \geq -18 mmHg) according with their blood pressure changes (*i.e.*, particularly decreases) as previously have been reported²⁹. Linear regression was applied in the backward mode for testing those potential body composition, metabolic and physical condition outcomes predictors outcomes of the PEH. The $\sum\Delta$ SBP decreases an average of the session 1 and 2 of both ET+RT and RT+ET groups related to the PEH (*i.e.*, decreases in SBP) was used as ‘dependent’ outcome, while age, height, body mass, BMI, waist circumference, body fat in % and kg, lean mass, skeletal muscle mass, bone mass, total body water, BMR, SBP, DBP, HR at rest, pulse pressure, fasting glucose, total cholesterol, LDL-c, HDL-c cholestetrol, triglycerides, 6Mwt, and handgrip muscle strength (dominan, and non-dominant arm) were used as ‘independent’ predictors. Statistical analyses for these procedures were applied using SPSS software version 28 (SPSSTM Inc., Chicago, Illinois, USA). The alpha level was fixed at ($p < 0.05$) for all tests of statistical significance.

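### The plan claims the CONSORT standard for randomised trials, but order was assigned by convenience, so the unadjusted ET+RT versus RT+ET comparison cannot isolate an effect of order

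*Combined protocol and SAP*

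**What the plan says.** All references are to the combined protocol and SAP.

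- **End of Scientific background:** "This study will follow the CONSORT guidelines for randomised trials". Shortly before this, the text gives exercise order as one motivation: "there is little knowledge about the role of the order".
- **Design:** "A quasi-experimental clinical study".
- **Methods:** recruited patients are those "who were assigned for convenience in 1:1 allocation to a CT group" in one of two orders. The groups are reported as "ET+RT; $n=17$; BMI 47.8 ± 16.7" and "RT+ET; $n=13$; BMI 43.0 ± 8.0". Recruitment ran over 2020 and 2021.
- **Statistical Analysis Plan:** a two-way ANOVA (group x time) with a post hoc test looks for "potential differences between ET+RT vs. RT+ET". Pre-post changes in SBP, DBP, MAP, HR and PP are then used "to test by the independent Student *t*-test differences between groups", with a Wilcoxon alternative. No covariate is named for either analysis.
- **Same section:** a backward regression relates the SBP fall, averaged over two sessions and taken across both groups, to a list of baseline measures. Group is not on that list.

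**The concern.** The reporting standard and the assignment method do not fit together. A reader told that the study follows the guideline for randomised trials will expect groups that differ only by chance at baseline. Convenience assignment gives no such assurance. The documents do not say who placed patients, on what basis, or in what sequence over the two years. Placement could have followed availability, fitness or calendar period; these are possibilities, not documented facts.

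What is at stake is the meaning of the between-order result. The Scientific background itself reports that the SBP fall after exercise is larger in people with higher blood pressure, so the make-up of each group can affect its mean change. The planned order tests do nothing to account for that, and the regression cannot do so because it does not contain group.

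**Working it through.** The plan gives no sample size calculation, power or outcome SD, so there is no design figure to reproduce. The main check is textual; the arithmetic shows what the reported group data can and cannot tell us.

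**1. The statements side by side.** The text before Design adopts a randomised-trial standard. Design says quasi-experimental. Methods says convenience. No random sequence, concealment or other random element is described. The first statement conflicts with the other two.

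**2. Group sizes.** Inputs: 17 and 13 (Methods). Exact 1:1 would give 15 and 15, so each group is off by 2. Under simple 1:1 randomisation of 30 patients, the probability of a split at least this uneven is 2 x P(X ≥ 17), with X binomial (30, 0.5), which is 0.58. The counts are uninformative about how assignment was done.

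**3. Baseline BMI.** Inputs: 47.8 (SD 16.7, n=17) and 43.0 (SD 8.0, n=13), from Methods.
- Difference: 47.8 − 43.0 = 4.8 kg/m².
- Pooled SD: √[(16 x 16.7² + 12 x 8.0²)/28] = 13.7. Standardised difference: 4.8/13.7 = 0.35.
- Welch SE: √(16.7²/17 + 8.0²/13) = 4.62; t = 4.8/4.62 = 1.04 on 24.1 df; p = 0.31; 95% CI −4.7 to 14.3.
- Chance range of a standardised difference under randomisation: ±1.96 x √(1/17 + 1/13) = ±1.96 x 0.368 = ±0.72. The observed 0.35 lies well inside it.
- The spreads differ more: variance ratio (16.7/8.0)² = 4.36, F-test p = 0.014. That test assumes normality, which is doubtful for BMI cut off at 40, so I put no weight on it.

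The mean gap does not show selective placement.

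**4. Consequence of an assumed bias.** Let b be the difference in mean SBP change produced by placement alone, in SD units of the change, with no true order effect. The t statistic is then noncentral on 17 + 13 − 2 = 28 df, with noncentrality b/√(1/17 + 1/13) = b/0.368. The SAP sets alpha at 0.05 without stating sidedness; two-sided is assumed.

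| Assumed b (SD) | Noncentrality | Chance of p < 0.05 with no order effect |
|---|---|---|
| 0 | 0 | 5.0% |
| 0.1 | 0.27 | 5.8% |
| 0.2 | 0.54 | 8.2% |
| 0.3 | 0.81 | 12.3% |
| 0.5 | 1.36 | 25.9% |

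The documents give no value for b. The table is a scale, not an estimate.

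**The case against.** The strongest reply is that nothing is hidden. The formal design label is quasi-experimental, the convenience assignment is stated openly, and CONSORT is a reporting guideline. The SAP speaks only of potential differences between the groups and nowhere commits to a causal conclusion about order. The title and much of the SAP concern individual response, and order appears as a knowledge gap, not as a declared primary comparison. All of this stands. It limits the point to a conflict of labels and an unprotected contrast, but removes neither: the order comparison is planned and tested, and the randomised-trial statement is current text.

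A reader might infer more than the documents support:

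- **That the 1:1 wording or the 17/13 split is part of the contradiction.** A ratio makes no claim of randomisation, and the split is unremarkable.
- **That selective placement has been shown.** It has not. The case rests on the stated assignment method, not on the observed groups.
- **That the p-values are meaningless.** The tests still address a difference in group means. What fails is reading that difference as caused by order.
- **That the bias can be put in mmHg.** The Scientific background gives gaps in SBP fall of 16.1 − 5.6 = 10.5 mmHg (ET) and 12.0 − 4.0 = 8 mmHg (RT) between higher-pressure and healthy subjects. An assumed imbalance of 20 to 30 percentage points would give 0.2 x 8 = 1.6 to 0.3 x 10.5 = 3.2 mmHg. But the ET pair comes from two separate cited studies, neither pair concerns concurrent training or morbid obesity, and no such imbalance is documented. Blood pressure is also measured here, so adjustment could address that route.

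**Conclusion.** The point holds in a limited form. The plan claims a randomised-trial standard that its design does not meet, and its between-order analysis has no protection against confounding by who was placed in which group or when. The within-group changes and the responder categories are not affected by this fault, because they do not rely on comparable order groups.

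The size and direction of any bias are unknown. Under an assumed bias of 0.2 to 0.5 SD of the change score, with a two-sided test, the false-positive rate for an order effect would be about 8% to 26% instead of 5%. The conclusion also takes the documents at their word: no random element is described, which is not proof that none was used.

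**What to change.** 1. Remove the statement that the study follows CONSORT for randomised trials, and report a non-randomised comparison under a standard meant for such studies.
2. State how patients were placed in each order, by whom, and in which period of 2020 to 2021.
3. Add a baseline-adjusted order comparison, for example ANCOVA of post-exercise SBP on group with baseline SBP and BMI. Both covariates are already collected, and two are modest for 30 patients. Say explicitly that this does not remove unmeasured confounding.
4. Word any ET+RT versus RT+ET difference as an association, not an effect of order.
5. If any patients remain to be assigned, use a concealed computer-generated list. The past tense and reported group sizes suggest that assignment is complete, in which case this step does not apply.

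Items 1, 2 and 4 are wording and reporting. Item 3 is one further model per outcome. The real cost is a weaker order claim, which is the claim the design can support.

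### No blood-pressure or antihypertensive-treatment condition is stated at entry, and the SAP uses neither hypertension diagnosis nor treatment, so responder labels can partly reflect blood-pressure class

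*Combined protocol and SAP*

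**What the plan says.** **Entry.** The Methods section gives morbid obesity, inactivity, a BMI of 40 kg/m² or more, and patients "aged 30 to 55 years) that were under the OBEMOB institution, who were assigned for convenience". The text mentions no blood-pressure range, hypertension status or drug treatment. The arms are ET+RT (n = 17) and RT+ET (n = 13).

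**Background.** The Scientific background calls hypertension and type 2 diabetes "two major diseases in the modernity, and of high prevalence in populations with excessive of adiposity such as those with morbid obesity". It says the fall after a single endurance session is "superior in subjects with higher blood pressure (systolic [SBP]/diastolic [DBP] $-16.1/-7.5$ mmHg") and "less marked in healthy normotensive subjects (SBP/DBP $-5.6/-3.1$ mmHg"). For resistance exercise it reports a larger fall "in subjects with elevated (SBP/DBP $-12.0/-4.0$ mmHg), than healthy subjects (SBP/DBP $-4.0/-1.0$ mmHg"). It also mentions "those with HTN controlled and HTN not so controlled", without figures for either.

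**Analysis.** The Statistical Analysis Plan sorts participants into nonresponders, low, moderate and high responders with systolic cut-points at −1, −10 and −18 mmHg. It compares the arms by two-way ANOVA and by a t-test on the change, with no covariate. It then runs a backward linear regression of ΣΔSBP on 24 candidates. These include SBP, DBP and "HR at rest, pulse pressure, fasting glucose, total cholesterol, LDL-c", but neither hypertension diagnosis nor antihypertensive treatment.

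**The concern.** The trial asks why patients with morbid obesity differ in their fall in blood pressure after exercise. By the protocol's own account, one known source of difference is the blood-pressure class a patient starts in. The bands ignore that class entirely. The regression sees it only through resting pressures, which backward selection may drop. Treatment appears nowhere, so a controlled, treated hypertensive and a normotensive patient with the same resting pressure look alike to every planned analysis.

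Two readings are then at risk. A high-responder or nonresponder label may be taken as individual responsiveness when it partly reflects blood-pressure class. And because allocation was by convenience, an imbalance in hypertension or treatment between the arms could enter the ET+RT versus RT+ET contrast with nothing in the plan to show or adjust for it.

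**Working it through.** The plan gives no figure of its own on this point, so there is none to reproduce. The check places the background's mean falls in the SAP's bands.

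**Inputs from the documents.** Mean SBP change after endurance exercise: −16.1 (higher pressure) and −5.6 (normotensive). After resistance exercise: −12.0 (elevated) and −4.0 (healthy). Cut-points: −1, −10, −18. I read the lowest band as a fall of less than 1 mmHg, which is clearly the intent.

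**Assumptions.** Normally distributed change; SD between patients of 5 to 12 mmHg (none is given); bands applied to a single-session change.

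**Means alone.** −5.6 and −4.0 both fall in the low band; −16.1 and −12.0 both fall in the moderate band.

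**Moderate or high response.** P(Δ ≤ −10) = Φ((−10 − μ)/SD).
- Endurance, SD 5: Φ(6.1/5) = Φ(1.22) = 0.89 vs Φ(−4.4/5) = Φ(−0.88) = 0.19.
- Endurance, SD 12: Φ(0.51) = 0.69 vs Φ(−0.37) = 0.36.
- Resistance, SD 5: Φ(2/5) = Φ(0.40) = 0.66 vs Φ(−6/5) = Φ(−1.20) = 0.12.
- Resistance, SD 12: Φ(0.17) = 0.57 vs Φ(−0.50) = 0.31.

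**Nonresponse.** P(Δ > −1) = 1 − Φ((−1 − μ)/SD), same SD range.

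| Figures used | Fall ≥ 10 mmHg: higher BP | Fall ≥ 10 mmHg: normal BP | Fall < 1 mmHg: higher BP | Fall < 1 mmHg: normal BP |
|---|---|---|---|---|
| Endurance | 69–89% | 19–36% | 0–10% | 18–35% |
| Resistance | 57–66% | 12–31% | 1–18% | 27–40% |

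The ratio for a fall of 10 mmHg or more runs from 57/31 = 1.8 to 66/12 = 5.5, depending on the SD.

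**How well resting SBP stands in for status.** Suppose half the sample has the status, resting SBP has SD 12 within each half, and the halves differ by g mmHg at rest. After regression on resting SBP, the share of any status gap in ΔSBP left in the residuals is 144/(144 + g²/4). For g = 0, 5, 10 and 20 this is 100%, 96%, 85% and 59%. The closer treatment brings resting pressure to normal, the less resting SBP can stand in. This says nothing about whether a treated-patient gap exists or how large it is.

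**Arm contrast.** If 60% of one arm and 40% of the other had higher pressure (an illustration; no split is given), the unadjusted difference would shift by 0.2 × 8.0 = 1.6 to 0.2 × 10.5 = 2.1 mmHg, where 8.0 = 12.0 − 4.0 and 10.5 = 16.1 − 5.6.

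**Room in the regression.** 30 − 24 − 1 = 5 residual degrees of freedom with all candidates in.

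**The case against.** The strongest reply is that the calculation measures something the plan already has. The background's contrasts are by blood-pressure level, and SBP, DBP and pulse pressure are on the predictor list. That stands for the regression: untreated high pressure is partly represented there. It does not help the bands or the arm comparisons, which use no baseline information, and it does not reach treated patients with controlled pressure.

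The background figures are also imperfect inputs. They come from single-mode sessions, not the concurrent session studied here. The endurance pair comes from two different studies and is introduced as an effect on 24 h pressure. By their titles, the study cited for −16.1 was in type 2 diabetes with prehypertension, and the one cited for the normotensive figure also names prehypertension. All of this stands, so the percentages are illustrative.

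The scale is uncertain too. The SAP speaks of a sum of ΔSBP when defining the bands and of an average of sessions 1 and 2 in the regression. An average keeps the means used above; a two-session sum would change the shares completely.

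Finally, a larger fall in hypertensive patients is real variation between individuals, not misclassification. That is fair. The fault lies in being unable to tell that source of variation from others.

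A reader might go further and infer that the band shares show a medication effect, or that resting heart rate or glucose would be selected because it marks a drug. The documents give no treated-versus-untreated figure and say nothing about drug effects on these measures. A reader might also infer that all blood-pressure classes were eligible. The entry description is brief and has no exclusion list, so one can say only that no condition is stated.

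**Conclusion.** The concern holds in limited form. No blood-pressure or treatment condition is stated at entry, and neither hypertension diagnosis nor antihypertensive treatment enters the bands, the arm comparisons or the 24 predictors, although the protocol itself expects hypertension to be common and falls to be larger at higher pressure. Band labels can therefore partly reflect blood-pressure class. The size, roughly a 1.8- to 5.5-fold difference in the chance of a moderate or high label, applies to the bands only. It rests on the background's single-mode means, a normal model, an assumed SD of 5 to 12 mmHg and a single-session reading of the bands.

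For treatment, the finding is that a plausible confounder is unrecorded in the analysis and that resting pressures cannot replace it where pressure is controlled. Its effect cannot be sized from the documents, and nothing shows that the arms were in fact unbalanced.

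**What to change.** 1. Record hypertension diagnosis (yes/no) and antihypertensive treatment (yes/no) for the 30 participants, from existing records or by asking them.
2. Report both by arm and by responder band, as counts only. A finer split would be too thin: four bands by three classes (normotensive, treated, untreated) gives 12 cells, or 30/12 = 2.5 patients per cell on average.
3. Put antihypertensive treatment into the ΣΔSBP regression in place of pulse pressure, and keep it in the model throughout backward selection. Pulse pressure is SBP minus DBP, so it adds nothing once both are listed, and the list stays at 24.
4. Repeat the ET+RT versus RT+ET comparison of ΔSBP adjusted for baseline SBP and treatment, as a sensitivity analysis. With arm, two covariates and an intercept this leaves 30 − 4 = 26 residual degrees of freedom. An analysis restricted to untreated patients is not advised, since it could leave very few per arm.

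The cost is a small data-collection effort. The treatment estimate will be imprecise at n = 30 and should be reported as such.
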